9.9 *Early Termination Study Visit:* If a participant decides to withdraw from the study after randomization or is terminated by the site principal investigator for any reason after randomization, an early termination study visit will be conducted to close out the participant from the study. At this visit the participant will be instructed to return all unused study medication. The Week 9 procedures will be attempted at an early termination visit, which will be conducted per Section 9.7.1, both in person and remotely.

10.0 ASSESSMENTS:

Every effort should be made to ensure that protocol-required tests and procedures are completed as described. When a protocol-required test cannot be performed, study staff will be instructed to document the reason for the missed test and any corrective and preventative actions which s/he has taken to ensure that required processes are adhered to as soon as possible. Any protocol deviations should be documented in the study log.

10.1 Blood: Total blood sampling volume for the individual participants is approximately 420 mL over approximately 14 weeks of the study. The actual times of blood sampling may change. Additional blood samples may be taken for safety assessments at times specified by the Coordinating Center, provided the total volume taken during the study does not exceed 450 mL (safety, PF-04457845 levels, endocannabinoid levels).

10.2 Safety:

10.2.1 Laboratory Tests: The following safety laboratory tests will be performed at the following study visits: Screening, Week 1, Week, 5, Week 7, Week 9, and End of Study Visit (end of Week 12). They are conducted periodically throughout the duration of the study to monitor electrolyte and liver/kidney function. Additional laboratory results may be generated on the samples (without additional blood volume drawn) as a result of the method of analysis, the type of analyzers used, or as derived or calculated values; if such results are available, they may also be reported. Unscheduled clinical labs may be obtained at any time during the study to assess any perceived safety concerns.

Hematology: Hemoglobin, Hematocrit, RBC Count, MCV, MCHC, RDW, MCH, MPV, Platelet Count, WBC Count, Total Neutrophils (Abs), Eosinophils (Abs), Monocytes (Abs), Basophils (Abs), Lymphocytes (Abs); Collected using one 10cc Lavender-top Tube (tube contains EDTA as an anticoagulant).

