Chemistry: BUN and Creatinine, BUN/Creatinine Ratio, Glucose, Calcium, Sodium, Potassium, Chloride, Total CO2, AST, ALT, Total Bilirubin, Direct Bilirubin, Alkaline Phosphatase, Urine acid, Albumin, Total protein, HDL, LDL, Cholesterol; Collected using one 10 cc Tiger-top Tube (tube does not contain an anticoagulant but does contain a clot activator and serum separator gel).

Urinalysis: Color, Appearance, Specific Gravity, pH, Glucose, Protein, Blood, Ketones, Nitrites, Leukocyte esterase, Bilirubin, Urobilinogen, Bacteria, Casts, Crystals, Yeast, Amorphous Sediment, Epithelial Cells, WBC, RBC; Collected using one 10cc urinalysis preservative tube (tube includes a preservative of chlorhexidine, ethylparaben, and sodium propionate).

On-Site Urine Drug Testing: At every study visit, participants will be tested using a urine drug quick dip. A 12-panel all-in-one drug test cup with a built-in temperature strip (CLIA waived) should be used for these quick dip urine drug tests. The minimum requirement for drug testing includes:

- 1. Amphetamines (Detection Period: 1-2 days; Cutoff Level: 1000 ng/mL)
- 2. Barbiturates (Detection Period: 1-4 days; Cutoff Level: 200 ng/mL)
- 3. Buprenorphine (Detection Period: 1-3 days; Cutoff Level: 10 ng/mL)
- 4. Benzodiazepines (Detection Period: 1-2 days; Cutoff Level: 200 ng/mL)
- 5. Cocaine (Detection Period: 2-4 days; Cutoff Level: 300 ng/mL)
- 6. THC-COOH (Detection Period: up to 5+ days; Cutoff Level: 50 ng/mL)
- 7. Methamphetamines (Detection Period: 2-4 days; Cutoff Level: 500 ng/mL)
- 8. Methylenedioxymethamphetamine (Detection Period: 2-4 days; Cutoff Level: 1000 ng/mL)
- 9. Methadone (Detection Period: 1-3 days; Cutoff Level: 300 ng/mL)
- 10. Opiates (Detection Period: 2-3 days; Cutoff Level: 300 ng/mL)
- 11. Oxycodone (Detection Period: 1-3 days; Cutoff Level: 100 ng/mL)
- 12. Phencyclidine (Detection Period: 7-14 days; Cutoff Level: 25 ng/mL)

If during the in-person visits a sample tests positive for any drug (other than THC) on site, a sample will be sent to the laboratory for confirmation.

Participants may undergo random urine drug testing at the discretion of the investigator. Spot urine drug testing conducted prior to dosing must be positive for cannabinoids for participants to receive study medication.

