10.3.1 PF-04457845 Levels: Blood will be sampled for PF-04457845 levels as specified in the Schedule of Procedures (1.5 Schedule of Procedures: Table 2). Given that adherence will be confirmed visually, the PF-04457845 levels will be assayed in only a random sampling of approximately 1/3 of participants from each site to confirm adherence, as specified by the Coordinating Center. Assays will be conducted by laboratory of [name] at Northeastern University using a proprietary assay with existing permission from SpringWorks and Jazz Pharmaceuticals. The serum sample to be analyzed for PF-04457845 levels should be collected in one 4 cc lavender top tube (tube containing K2-EDTA). Blood samples should be collected as close to approximately 1 hour after the participant has taken their daily dose of study medication (PF-04457845/placebo). The time at which the blood sample has been drawn at should be documented, along with the time that the study medication was taken that day. The sample should then be centrifuged at approximately 1700g for about 10 minutes at 4 degrees Celsius, pipetted into appropriately labeled 1.5 mL screw capped polypropylene tubes (1 mL of serum sample per tube; 2 polypropylene tubes), and then stored in a -80 degree Celsius freezer within 1 hour of collection. Samples will be stored on site until they are to be sent directly to WuXi by each site, at the end of the study.

Shipment of Pharmacokinetic Samples: Each site will store blood samples to be assayed for PF-04457845 levels on site in a -80 degree Celsius freezer. Samples will be stored on site, and will be shipped on dry ice directly to the lab of [name] at Northeastern University, in batches of at least 50 samples. The Coordinating Center will instruct each individual site on which random sampling of participants should be shipped.

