10.3.2 Plasma Anandamide Levels: Blood will be sampled for plasma anandamide and other

endocannabinoid levels as specified in the Schedule of Procedures (**1.5** Schedule of Procedures:

Shipment of Plasma Anandamide Samples: Each site will store blood samples to be assayed for anandamide levels on site at -80 degree Celsius. Samples will be shipped on dry ice directly to the lab of [name] at Northeastern University, approximately every 6 months.

10.3.3 DNA: A single nucleotide polymorphism (SNP) in the gene encoding for FAAH - C385A variance was reported to be significantly associated with changes in withdrawal after abstinence, and happiness after smoking cannabis (206-208). Recently, 3 specific CUD risk alleles were reported for the first time in a Yale-led study by Gelernter et al., 216 (209). These included rs143244591 in novel antisense transcript RP11-206M11.7; rs146091982 in the solute carrier family 35 member G1 gene (SLC35G1); and rs77378271 in the CUB and Sushi multiple domains 1 gene (CSMD1). These and other genes will be studied in an exploratory manner to examine for genetic moderators of response to PF-04457845. DNA will be sent to the laboratory of [name] at Yale.

One 10cc PAXgene Blood DNA tube (sterile vacutainer plastic tube with hemogard closure and K3 EDTA additive) should be collected for DNA analysis for all participants at the screening visit and appropriately labeled. Each sample should be frozen first at -20 degrees Celsius for 24 hours, and then transferred to a -80 degree Celsius freezer, in the original 10cc tube that it was collected in.

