11.1.2 Cannabis Withdrawal Symptoms: The typical withdrawal symptoms in humans include: cannabis craving, anger, aggression, appetite change, weight loss, irritability, anxiety, restlessness, altered sleep, strange dreams and physical discomfort (39, 40, 99, 225). Less common symptoms include: chills, depressed mood, stomach pain and sweating. Most symptoms appear within 1 day of abstinence, peak within 2–3 days, and resolve within 1–2 weeks. Two studies evaluated symptom time course for at least four weeks (45 days and 28 days, respectively). Both studies observed prominent withdrawal symptoms during the initial two to three weeks of abstinence, some of which persisted through the entire study period (63, 70). The findings of these studies suggest that withdrawal symptoms may persist longer than 4 weeks. Characteristic of a true withdrawal syndrome, abstinence symptoms occur with blind discontinuation and resolve with CB1R agonist re- administration. Finally, the administration of cannabis or THC attenuates withdrawal symptoms.

These symptoms that people experience when they stop smoking marijuana are uncomfortable but not life threatening. The marijuana withdrawal symptoms will be monitored closely. If intolerable, participants will be able to withdraw from further study participation.

11.1.3 Phlebotomy: Bruising, infection and thrombosis can occur during phlebotomy. These risks can be minimized by having these procedures performed by experienced personnel using good clinical technique. Participants will have no more than 3 oz. of blood drawn over the entire study period. These amounts are well within the Red Cross blood standards.

11.1.4 Behavioral/Cognitive Testing: Some participants may experience the behavioral as boring or frustrating. Trained research staff will work closely with participants and if necessary provide them with breaks.

11.2 Known Potential Benefits: Study participation may facilitate a reduction of cannabis use for study participants. Group data collected from this study will also inform the development of

this drug for the treatment of CUD, for which there are no currently approved pharmacological treatments.

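### Section 11.1.3 limits blood to 3 oz (about 89 mL) over the study, but Section 10.1 plans about 420 mL and the scheduled safety tubes alone come to 120 mL

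*Combined protocol and SAP*

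**What the plan says.** Section 11.1.3 (Phlebotomy, under Known Potential Risks) states: "Participants will have no more than 3 oz. of blood drawn over the entire study period". The sentence after it describes these amounts as comfortably within Red Cross standards.

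Section 10.1 (Blood) states: "Total blood sampling volume for the individual participants is approximately 420 mL over approximately 14 weeks of the study". It permits further safety samples "provided the total volume taken during the study does not exceed 450 mL".

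The components are given in several places:

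- Section 10.2.1 schedules safety laboratory tests at six visits: Screening, Weeks 1, 5, 7 and 9, and End of Study. The chemistry and hematology row of Table 2 marks the same six. Hematology is "Collected using one 10cc Lavender-top Tube" and chemistry is "Collected using one 10 cc Tiger-top Tube".
- Section 10.3.3 requires, at screening, "One 10cc PAXgene Blood DNA tube".
- Section 10.3.1 says the drug-level sample "should be collected in one 4 cc lavender top tube". Section 7.6.2 and Table 2 place these draws at Weeks 1, 5 and 9. Section 9.7.3 also lists a drug-level and endocannabinoid draw at End of Study, which Table 2 does not mark.
- Section 10.3.2 provides for endocannabinoid sampling, but the available text gives no tube volume.

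**The concern.** Sections 10.1 and 11.1.3 both describe the total taken from one participant over the whole study, and they differ nearly five-fold. The wording of 11.1.3 covers the entire study, so it cannot be read as a per-visit figure. Both statements are in running prose, so the conflict does not come from a broken table.

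What is at stake is the accuracy of the risk description. The Red Cross reassurance is attached to the 3 oz figure and has not been shown for the volume that Section 10.1 plans. The protocol treats blood volume as relevant to risk: Section 10.1 sets a ceiling, and Section 11.4.3 makes recent blood donors wait eight weeks before taking part.

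**Working it through.** **Conversions.** The factor 29.57 mL per US fluid ounce is a unit conversion and does not come from the protocol.

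- Stated maximum: 3 × 29.57 = 88.7 mL. With imperial ounces (28.41 mL) it is 85.2 mL.
- Planned total: 420 / 29.57 = 14.2 oz, and 420 / 88.7 = 4.7 times the maximum.
- Ceiling with extra samples: 450 / 29.57 = 15.2 oz.

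**Volume from the tube list.** The formula is the sum of nominal tube volume × number of scheduled draws. Endocannabinoid tubes are counted as 0 mL because their volume is not available, so the result is a lower bound.

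- Safety tubes: 6 × (10 + 10) = 120 mL, or 4.1 oz. This alone exceeds 88.7 mL.
- DNA tube: 1 × 10 = 10 mL.
- Drug-level tubes: 3 × 4 = 12 mL, or 4 × 4 = 16 mL with the End of Study draw.
- Total: 120 + 10 + 12 = 142 mL (4.8 oz, 142 / 88.7 = 1.6 times the maximum), or 120 + 10 + 16 = 146 mL (4.9 oz).

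**Where the maximum is passed.**

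| Visit | Drawn (mL) | Running total (mL) |
|---|---|---|
| Screening | 20 + 10 | 30 |
| Week 1 | 20 + 4 | 54 |
| Week 5 | 20 + 4 | 78 |
| Week 7 | 20 | 98 |
| Week 9 | 20 + 4 | 122 |
| End of Study | 20 (+ 4) | 142 (146) |

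The running total passes 3 oz at Week 7, with either ounce.

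**Sensitivity to tube fill.** The twelve safety tubes would fit within 3 oz only at 88.7 / 12 = 7.4 mL or less each, with nothing else drawn.

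**Comparison with 420 mL.** The listed tubes leave 420 − 142 = 278 mL, or 420 − 146 = 274 mL, unaccounted for. If endocannabinoid tubes alone made up the difference, each draw would need 278 / 3 = 92.7 mL or 274 / 4 = 68.5 mL.

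**The case against.** The best case against this point accepts the contradiction and disputes what can be built on it.

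**That 420 mL is also wrong.** A reader might infer this because the listed tubes reach only about a third of that total. The documents do not support it. The text of Section 10.3.2 breaks off where its sister section on drug levels gives tube type and volume, so the endocannabinoid details may have been lost in extraction. Serum inflammatory biomarkers (Section 4.1.2, objective 15) and stored biosamples (Section 17.6) are planned without a listed volume. Section 17.2 mentions RNA as well as DNA. Section 10.2.1 allows unscheduled laboratory tests and a 10 cc serum pregnancy test when the urine test is positive. This objection stands: the visible list is a lower bound. A gap of 274 to 278 mL justifies a question to the sponsor, not a finding of error.

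**That sites would omit safety tests to stay within 3 oz.** This too might be inferred, but 11.1.3 is a descriptive sentence in a risk paragraph. Table 2 and Section 10 govern the draws, and nothing tells a site to withhold tests at 3 oz. This objection also stands.

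**That ethics review or participants were misled.** The review board receives the whole protocol, including Section 10.1 (Section 17.1). The consent form is not in the reviewed text, so what participants are told cannot be checked.

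None of this rescues the 3 oz figure. Every omitted component would add volume. Partial fill would have to be substantial to bring even the safety tubes under 3 oz, and it would widen the distance to 420 mL.

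**Conclusion.** The 3 oz statement in Section 11.1.3 is wrong as written. It conflicts with the Section 10.1 total by a factor of 4.7, and with the protocol's own tube list by a factor of at least 1.6 (142 mL against 88.7 mL). Nothing in the protocol reconciles these figures. The 1.6 assumes nominal fill and counts endocannabinoid tubes as zero; the 4.7 needs only the two stated totals and the unit conversion. The Red Cross reassurance is unsupported for the planned volume until it is rechecked.

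The conclusion goes no further than that. The 420 mL figure is unconfirmed, not refuted, and no effect on site conduct or on what participants were told has been shown. The point concerns the risk description and leaves the sample size, type I error and efficacy analysis untouched. It is worth correcting because it is a stated limit on participant burden that the scheduled draws cannot meet.

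**What to change.** Recompute the whole-study volume from the final schedule and all tube volumes. Include the endocannabinoid tubes and any biomarker or stored samples that need blood of their own. Settle whether the End of Study assay draw in Section 9.7.3 takes place, and make Table 2 agree. State the one resulting figure in both Section 10.1 and Section 11.1.3, and recheck the Red Cross statement against it. If the recount does not give about 420 mL, explain the difference or change that figure. Check the consent form for the same number.

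The passages must be reconciled with each other and with the tube list; this review does not propose a volume limit. The cost is a short recount and a wording amendment, with no change to design or analysis.

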12.0 ADVERSE EVENT REPORTING

An AE is defined as any untoward medical occurrence in a clinical investigation participant administered a drug; it does not necessarily have to have a causal relationship with this treatment. An AE can therefore be any unfavorable and unintended sign (e.g., a clinically significant abnormal laboratory value), symptom, or disease temporally associated with the use of a drug whether or not it is considered related to the drug. All observed or volunteered AEs regardless of treatment group or suspected causal relationship to the investigational product(s) will be reported as described in the following sections.

The site principal investigator will be responsible for monitoring the data and assuring protocol adherence. At a minimum of every six months (including when re-approval of the protocol is sought), each site should notify the Coordinating Center of all adverse events. The Coordinating Center will then conduct safety reviews across all sites participating in the study. During the review process, the study principal investigator and coordinating physician investigator (responsible for medical oversight) will evaluate whether the study should continue unchanged, require modification/amendment, continue or close to enrollment. Either the study principal investigator or institutional review boards overseeing the study have the authority to stop or suspend the study or require modifications.

For all AEs, the investigator must pursue and obtain information adequate both to determine the outcome of the AE and to assess whether it meets the criteria for classification as an SAE requiring immediate notification to the Coordinating Center. For all AEs, sufficient information should be obtained by the investigator to determine the causality of the AE. The investigator is required to assess causality. Follow-up by the investigator may be required until the event or its sequelae resolve or stabilize at a level acceptable to the investigator, and the Coordinating Center concurs with that assessment.

As part of ongoing safety reviews conducted by the Coordinating Center, any non-serious adverse event that is determined by the Coordinating Center to be serious will be reported by the Coordinating Center as a SAE. To assist in the determination of case seriousness further information may be requested from the investigator to provide clarity and understanding of the event in the context of the clinical trial.

12.1 Reporting Period: For SAEs, the active reporting period begins from the time that the participant provides informed consent, which is obtained prior to the participant's participation in the study, through the last follow up visit (end of study visit). Should an investigator be made aware of any SAE occurring any time after the active reporting period, it must be promptly reported.

12.2 Capturing Adverse Events: Safety and adverse events will be captured using the Systematic Assessment for Treatment Emergent Events (SAFTEE) general and specific inquiry forms, which take approximately 20 minutes to administer. Collection of adverse events will commence from the time the participant signs the informed consent to participate in the study and will continue until the last safety follow up visit. At each study visit, the investigator will

assess whether any subjective AEs have occurred. A neutral question, such as "How have you been feeling since your last visit?" may be asked. Participants may report AEs occurring at any other time during the study. All participants experiencing AEs, whether considered associated with the use of the study drug or not, must be monitored until the symptoms subside and any clinically relevant changes in laboratory values have returned to Baseline or until there is a satisfactory explanation for the changes observed. All AEs will be documented, whether or not the investigator concludes that the event is related to the drug treatment. Any medical condition that is present at the time that the participant is screened will be considered as baseline and not reported as an AE. However, if the study participant's condition deteriorates at any time during the study, it will be recorded as an AE.

The following information will be documented for each event:

- 1. Event term.
- 2. Start and stop date and time.
- 3. Pattern of AE (Frequency).
- 4. Intensity.
- 5. Investigator's opinion of the causal relationship between the event and administration of study drug(s) (related or not related).
- 6. Investigator's opinion of the causal relationship to study procedure(s), including the details of the suspected procedure.
- 7. Action concerning study drug.
- 8. Outcome of event.
- 9. Seriousness.

The different categories of intensity (severity) are characterized as follows:

- Mild: The event is transient and easily tolerated by the participant. The event does not
 generally interfere with usual activities of dailyliving.
- Moderate: An AE that is usually alleviated with additional specific therapeutic intervention. The event interferes with usual activities of daily living, causing discomfort but poses no significant or permanent risk of harm to the research participant.
- Severe: An AE that interrupts usual activities of daily living, significantly affects clinical status, or may require intensive therapeutic intervention, and are usually potentially life-threatening or incapacitating. The term "severe" does not necessarily equate to "serious".

Note the distinction between the severity and the seriousness of an AE. A severe event is not necessarily a serious event. For example, a headache may be severe (interferes significantly with participant's usual function) but would not be classified as serious unless it met one of the criteria for SAEs, listed above.

Action Concerning the Study Drug: For every adverse event, the action taken concerning the study drug will be documented on the source document.

- Drug withdrawn: a study drug is stopped due to the particular AE.
- Dose not changed: the particular AE did not require stopping a study drug.
- Unknown: only use if it has not been possible to determine what action has been taken.
- Not Applicable: study drug was stopped for a reason other than the particular AE (the study has been terminated, the participant died, dosing with study drug was already stopped before the onset of the AE)
- Dose Interrupted: the dose was interrupted due to the particular AE.

12.3 Assigning Causality of Adverse Events: Causality to study procedures should be determined for all adverse events. The degree of certainty about causality will be graded using

the categories below. In a clinical trial, the study product must always be suspect.

- Definitely Related There is clear evidence to suggest a causal relationship, and other
 possible contributing factors can be ruled out. The clinical event, including an abnormal
 laboratory test result, occurs in a plausible time relationship to study intervention
 administration and cannot be explained by concurrent disease or other drugs or
 chemicals. The response to withdrawal of the study intervention (dechallenge) should be
 clinically plausible. The event must be pharmacologically or phenomenologically definitive,
 with use of a satisfactory rechallenge procedure if necessary.
- Probably Related There is evidence to suggest a causal relationship, and the influence of other factors is unlikely. The clinical event, including an abnormal laboratory test result, occurs within a reasonable time after administration of the study intervention, is unlikely to be attributed to concurrent disease or other drugs or chemicals, and follows a clinically reasonable response on withdrawal (dechallenge). Rechallenge information is not required to fulfill this definition.
- Potentially Related There is some evidence to suggest a causal relationship (e.g., the event occurred within a reasonable time after administration of the trial medication). However, other factors may have contributed to the event (e.g., the participant's clinical condition, other concomitant events). Although an AE may rate only as "possibly related" soon after discovery, it can be flagged as requiring more information and later be upgraded to "probably related" or "definitely related", as appropriate.
- Unlikely to be related A clinical event, including an abnormal laboratory test result, whose temporal relationship to study intervention administration makes a causal relationship improbable (e.g., the event did not occur within a reasonable time after administration of the study intervention) and in which other drugs or chemicals or underlying disease provides plausible explanations (e.g., the participant's clinical condition, other concomitant treatments).
- Not Related The AE is completely independent of study intervention administration, and/or evidence exists that the event is definitely related to another etiology. There must be an alternative, definitive etiology documented by the clinician.

The investigator's assessment of causality must be provided for all AEs (serious and non-serious); the investigator must record the causal relationship in the CRF, as appropriate, and report such an assessment in accordance with the serious adverse reporting requirements if applicable. An investigator's causality assessment is the determination of whether there exists a reasonable possibility that the investigational product caused or contributed to an AE; generally the facts (evidence) or arguments to suggest a causal relationship should be provided. If the investigator does not know whether or not the investigational product caused the event, then the event will be handled as "related to investigator's causality assessment is "unknown but not related to investigational product", this should be clearly documented on study records.

In addition, if the investigator determines an SAE is associated with study procedures, the investigator must record this causal relationship in the source documents and CRF, as appropriate, and report such an assessment in accordance with the SAE reporting requirements, if applicable. Adverse events will be monitored for each participant participating in the study and attributed to the study procedures / design by the study principal investigator ([name]) according to the following categories:

- Definite: Adverse event is clearly related to investigational procedures(s)/agent(s).
- Probable: Adverse event is likely related to investigational procedures(s)/agent(s).
- Possible: Adverse event may be related to investigational procedures(s)/agent(s).
- Unlikely: Adverse event is likely not to be related to the investigational

procedures(s)/agent(s).

• Unrelated: Adverse event is clearly not related to investigational procedures(s)/agent(s).

12.4 Adverse Event Outcome: For every adverse event, the outcome must be documented in the source document as one of the following.

- Recovered/resolved participant returned to first assessment status with respect to the AE.
- Recovering/resolving the intensity is lowered by 1 or more stages; the diagnosis or signs/symptoms have almost disappeared; the abnormal laboratory value improved, but has not returned to the normal range or Baseline; the participant died from a cause other than the particular AE with the condition remaining "recovering/resolving".
- Not recovered/not resolved there is no change in the diagnosis, signs, or symptoms; the
 intensity of the diagnosis, signs/symptoms, or laboratory value on the last day of the
 observed study period has got worse than when it started; is an irreversible congenital
 anomaly; the participant died from another cause with the particular AE state remaining
 "not recovered/not resolved".
- Resolved with sequelae the participant recovered from an acute AE but was left with permanent/significant impairment (e.g., recovered from a cardiovascular accident but with some persisting paresis).
- Fatal the AEs are considered as the cause of death.
- Unknown the course of the AE cannot be followed up due to hospital change or residence change at the end of the participant's participation in the study.

The overall principal investigator will conduct a review of all adverse events upon completion of every study participant. The principal investigator will evaluate the frequency and severity of the adverse events and determine if modifications to the protocol or consent form are required.

12.5 **Pre-Existing Conditions:** Pre-existing conditions, present at the time of signing informed consent, are considered to be concurrent medical conditions and should not be recorded as adverse events. All pre-existing conditions and their severity need to be documented at the time of the screening visit. If the participant experiences a worsening or complication of such a concurrent medical condition, the worsening or complication should be recorded appropriately as an adverse event. Investigators should ensure that the event term recorded captures the change in the condition.

12.6 Worsening of Adverse Events: If the participant experiences a worsening or complication of an AE after the first administration of study drug or any change in study drug, the worsening or complication should be recorded as a new AE. Investigators should ensure that the AE term recorded captures the change in the condition (e.g., "worsening of...").

12.7 Serious Adverse Events: An SAE is defined as any untoward medical occurrence that at any dose:

- 1. Results in death.
- 2. Is life threatening.
 - The term "life threatening" refers to an event in which the participant was at risk of death at the time of the event; it does not refer to an event that hypothetically might have caused death if it were more severe.
- 3. Requires inpatient hospitalization or prolongation of existing hospitalization.
- 4. Results in persistent or significant disability/incapacity.
- 5. Is a congenital anomaly/birth defect.

6. Is an important medical event that a) may require intervention to prevent items 1 through 5 above, or b) may expose the participant to danger, even though the event is not immediately life threatening or fatal or does not result in hospitalization

Each adverse event is to be assessed to determine if it meets the criteria for a serious adverse event. An adverse event may be graded as severe but still not meet the criteria for a Serious Adverse Event. Similarly, an adverse event may be graded as moderate but still meet the criteria for an SAE. It is important for the PI to consider the grade of the event as well as its "seriousness" when determining whether reporting to the HIC or HSC is necessary.

Medical and scientific judgment is exercised in determining whether an event is an important medical event. An important medical event may not be immediately life-threatening and/or result in death or hospitalization. However, if it is determined that the event may jeopardize the participant or may require intervention to prevent one of the other AE outcomes, the important medical event should be reported as serious. Examples of such events are intensive treatment in an emergency room or at home for allergic bronchospasm; blood dyscrasias or convulsions that do not result in hospitalization; or development of drug dependency or drug abuse.

12.8 Follow-up of Serious Adverse Events: If information not available at the time of the first report becomes available at a later date, the investigator should complete a follow-up SAE form or provide other written documentation and notify the Coordinating Center within 24 hours of receipt. Copies of any relevant data from the hospital notes (e.g., ECGs, laboratory tests, discharge summary, postmortem results) should be sent to the addressee, if requested. All SAEs should be followed up until resolution or permanent outcome of the event. The timelines and procedure for follow-up reports are the same as those for the initial report.

12.9 Serious Adverse Event Reporting Requirements: If an SAE occurs, the Coordinating Center is to be notified within 24 hours of investigator awareness of the event, using a standard reporting form (e.g. local institutional SAE form, CIOMS, MedWatch 3500a, or similar), regardless of the suspected causal relationship between the SAE and the study drug. In particular, if the SAE is fatal or life-threatening, notification to must be made immediately, irrespective of the extent of available AE information. This timeframe also applies to additional new information (follow-up) on previously forwarded SAE reports. In the rare event that the investigator does not become aware of the occurrence of an SAE immediately (e.g., if an outpatient study participant initially seeks treatment elsewhere), the investigator is to report the event within 24 hours after learning of it and document the time of his/her first awareness of the AE. The Coordinating Center will submit any SAE report to Jazz Pharmaceuticals via email ([contact]) on behalf of the investigator within 1 business day after it was received at the Coordinating Center.

For all SAEs, the investigator is obligated to pursue and provide information to the Coordinating Center in accordance with the timeframes for reporting specified above. In addition, an investigator may be requested to obtain specific additional follow-up information in an expedited fashion. This information collected for SAEs is more detailed than that captured on the AE source document. In general, this will include a description of the AE in sufficient detail to allow for a complete medical assessment of the case and independent determination of possible causality. Information on other possible causes of the event, such as concomitant medications and illnesses must be provided. In the case of a participant death, a summary of available autopsy findings must be submitted as soon as possible to the Coordinating Center.

12.10 Pregnancy Reporting Requirements: In the case of a pregnancy in a female participant or a female partner of a male participant, the site must notify the Coordinating Center within 24 hours of awareness. The Coordinating Center will report to Jazz Pharmaceuticals via email

([contact]) using the Jazz Pregnancy Query Form within 1 business day after receiving notification from the site. The Pregnancy Query Form must be further completed and sent to Jazz Pharmaceuticals via email ([contact]) as additional details of the pregnancy become available, and at the time that the outcome of the pregnancy is known. The pregnancy should be followed up to determine outcome (including spontaneous or voluntary termination), details of the birth, and the presence or absence of any birth defects, congenital abnormalities, or maternal and/or newborn complications.

While pregnancy itself is not considered an AE or SAE, any pregnancy complications or elective termination of a pregnancy for medical reasons will be reported as an AE or SAE. An abnormal pregnancy outcome (e.g., spontaneous abortion, fetal death, stillbirth, congenital anomalies, ectopic pregnancy, etc.) are considered SAEs and will be reported as such.

